Preliminary work - Global COVID-19 and Asthma Study (GCAS). The proposed study builds on data collected from the GCAS, an ongoing cross-sectional online survey we launched in May 2020 to examine how the COVID-19 pandemic affected the prevalence of disinfectant use among adults with asthma and to assess the associations of the frequency of disinfectant use with asthma control as measured by the Asthma Control Test (ACT). To date, over 1000 individuals have responded. Of those, 92% are based in the US, 80% are female, about 21% indicated minority race/ethnicity, and 625 agreed to be contacted for follow-up research. Of those willing to be contacted about, 40% had ACT≤19. About 95% of respondents reported increased hand washing, 88% increased use of alcohol-based hand sanitizer since the

[figure not shown]
[figure not shown]

Figure 2. Household use of Disinfectants ≥5 Times/Week prior To and Since COVID-19

COVID-19 pandemic (Figure 2); about one-third noted increased smoking behaviors by household members. The percentage of participants reporting household use of disinfectant wipes, disinfectant sprays, and a bleach and water solution to disinfect objects ≥ 5 times per week more than doubled since COVID-19. We observed statistically significant associations of the increased frequency of household disinfectants use since COVID-19 with reduced asthma control (ACT score ≤ 19).

Chicago Asthma Consortium (CAC) was formed in 1996 by American College of Chest Physicians and Respiratory Health Association to coordinate the activities of the asthma community in Chicago. One priority of the CAC is the coordination of the Community Advisory Board (CAB), which was formed in 2014 with support from several grants. The CAB is comprised of community health workers, parents, patients, and pastors from the communities that have the highest asthma rates in Chicago. The research team met with the 5 members of CAC on Wednesday August 5, 2020. The study was briefly explained to CAC members and feedback was received related to all aspects of the proposed protocol including adding an instructional video, reducing the routine EMA notifications from 3 to 2X/day, the 14-day data collection length, and assuring a research team member was available for troubleshooting. Suggestions were incorporated into the study procedures. Once funded, we will meet with the CAC semi-annually for input and feedback on study protocols, measures, recruitment, and interpretation of findings.

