Research Design. This study will evaluate the feasibility and usability of assessing real-time residential environmental exposures (VOCs/PM_{2.5}), asthma symptoms, and lung function using an innovative combination of commercially available technology (Aim 1).⁶⁰ In addition, we will use observational design to explore the unintended effects of these residential environmental exposures on adults with poorly controlled asthma in the era of COVID-19 (Aims 2 & 3).

Sample. Eligibility criteria include GCAS participants who: (1) indicated willingness to be contacted for future research, (2) reported high use of disinfectant/cleaning products since COVID-19 (≥ 5 per week), and current ACT ≤ 19 . Non-US residents and non-English speakers will be excluded. We will strive to have at least 20% of the sample representing minority populations. Fifty individuals meeting these criteria will be randomly selected and invited to participate in this study using their preferred contact method (94% indicated email). Interested individuals will be directed to a REDCap survey link to confirm willingness to participate, verify eligibility, and provide current contact information. We will randomly select replacements if no response is received after 2 contact attempts over two weeks or lack of interest is indicated.

Data collection methods. Three innovative data collection methods will be integrated in this feasibility study: Ecological Momentary Assessment (EMA) downloaded to participants' smartphone, Awair Omni Indoor Air Quality Monitor®, and Zephyr_x Spirometer.

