Zephyr_x Spirometer⁷² system allows for laboratory quality pulmonary function tests (PFTs) at home (FVS-forced vital capacity, FEV₁-forced expiratory volume in 1 second, FEV₁/FVC, flow-volume loop). The system consists of an FDA approved handheld Bluetooth spirometer (MIR Spirobank Smart), and a mobile application that works on a smartphone or tablet device. The MIR Spirobank bank measures 49x109x21 mm and weighs 60.7 g. Participants share PFT results through their app and researcher team members will access a HIPAA compliant portal to view participants' PFT results in real time. An in-App video coaching feature guides the participant through the PFT maneuver. Each maneuver conducted by the participant creates a time and date stamped American Thoracic Society standard PFT report accessible through the portal. Data will be exported from the dashboard to a .CSV file.

Procedures (Figure 3)

1. Randomly selected individuals from the CGAS study who meet eligibility criteria will be invited to participate in the current study. Those interested will be directed to a REDCap link to complete an E-consent form and baseline questionnaire.
2. An Awair Indoor Air Quality Monitor and a Zephyr_x Spirometer will be mailed to each participant along with a quick start guide, written instructions with a link to an instructional video, and research team contact information. Once received, a research team member will conduct a live chat with each participant to enable the devices, download apps (EMA, Zephyr_x), setup and test the devices and apps, review the protocol, and address questions. Participants will be instructed to place the portable Awair air quality monitor in the room where they spend the most time during the day and at night where they sleep.
3. A 3-day run-in period will be completed during which the participants will become familiar with the devices and troubleshoot issues (Awair requires 24-48 hours to calibrate VOC sensors). Study personnel will be available to answer questions/address technical issues. After the run-in period, a research team member will contact the participant to launch the 14-day data collection period.

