- *EMA survey triggered by VOCs/PM_{2.5} greater than optimal range as detected by the Awair* will query asthma symptoms, lists of probable sources of elevated VOCs or PM_{2.5}.
- *EMA survey 30-minutes after Awair air quality notification* queries mitigation strategies used (from lists) and asthma symptoms.
- *Home spirometer use* (Yes:No) queried in each EMA survey

Home spirometer. FEV₁% predicted– a standard metric of lung function for those with asthma.

Seven-Day check-in. Open-ended questions to identify any trouble-shooting areas, determine if adjustments need to be made, and assess ease of use of the app/devices. Interactions will be recorded and reviewed by the research team for patterns and to identify any adjustments that are needed.

Participant feasibility assessment. At the end of the 14-day data collection period, participants will be asked to respond to a short REDCap survey assessing acceptability, appropriateness, and feasibility of the indoor air quality monitor, EMA notifications, and the home spirometer with response ranging from 1=completely disagree to 5=completely agree. A random sample of 20 participants will be interviewed to further explore these factors using open-ended questions such as "Tell us what you liked/didn't like about the indoor air quality monitor", "Describe the strengths/concerns about the survey you received about your home indoor air quality".

Data Analysis

Each day of observation will be divided into four 4-hour periods between 6 a.m. and 10 p.m. Data from a given period will be considered as follows:

1. Period specific data from all event-contingent EMA prompts [prompts triggered by high indoor air VOC/PM_{2.5} readings] will be analyzed. If multiple event-contingent prompts were answered, data will be averaged across all event-contingent prompts during that period.
2. Data from all answered baseline and random [signal-contingent] EMA prompts will be considered.

Aim 1. For this aim, we will assess:

1. Compliance with the EMA prompts as indicated by the frequency of responses to prompts, specifically:
 - a. # of responses (complete:incomplete)/number of prompts
 - b. # times spirometer used/number of prompts
 - c. # times environment modified/number of event-contingent prompts
2. Compliance as described in 1a-1c by 4-hr each period.

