We will also assess the duration the indoor air quality monitor is used by each participant. The quantitative participant feasibility assessment of acceptability, appropriateness, and feasibility will be analyzed descriptively. In addition, we will examine differences in use/acceptance by participant characteristics (e.g., age, asthma symptoms, overall health, education, etc). Qualitative interview data will be transcribed, uploaded into Dedoose qualitative analysis software for content analysis.

Aim 2a: We will collect baseline data on the current frequency and degree of disinfectants/cleaners and exposure to environmental triggers (e.g., secondhand smoke). We will capture real-time self-reported data on disinfectant use throughout the study period. We will determine the prevalence of disinfectant/cleaner use and frequency (% EMA prompts at which disinfectant/cleaner use is reported). We will obtain data from the Awair dashboard to determine the number of times VOCs and PM_{2.5} levels exceed optimal levels, average daily levels, average levels per time period, and fluctuations in VOC and PM_{2.5}. We will identify possible environmental triggers that contribute to high levels of VOCs and PM_{2.5} leading to event-contingent prompts.

[figure not shown]
Aim 2b: We will determine baseline level of asthma control as measured by the ACT. We will use EMA to determine the level of asthma control over the study period as indicated by (a) asthma symptoms reported at each prompt and over the 14 days; (b) number of time-periods during which an EMA prompt is sent and participants report asthma symptoms; and (c) lung function as measured by FEV₁% predicted at each prompt. Asthma control will also be evaluated using EMA by exploring differences in variability in lung function.

Aim 3: Data collected using the EMA approach are multilevel with time windows (level 1) nested with individuals (level 2). The exposure variables will include: (1) Baseline self-reported use and frequency of disinfectant/cleaner use and PM_{2.5} exposures; (2) Number of times VOC and PM_{2.5} levels exceed the threshold for the optimal readings per week; and (3) Average scores of VOC and PM_{2.5} levels in the time windows considered in the analysis. The outcome variables we will consider include occurrence of any asthma symptoms, inhaler use, and FEV₁% predicted (within 30 minutes of each EMA prompt).

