We will use multi-level binary logistic regression to examine the associations of the exposure variables with the binary outcome variables. We will use multilevel linear regression to examine the associations of the exposure variables with FEV₁% predicted. We will control for level 1 variables (time of day, day of week) and level 2 variables (baseline asthma symptoms, demographic characteristics, and psychosocial characteristics). Using available time stamps from the indoor air quality monitor, EMA, and the spirometer, we will also explore average lag time between an event-contingent prompt and self-reported asthma symptoms using multilevel survival analyses.

Summary

The proposed study has several strengths. First, our study is innovatively addressing the increased use of disinfectants during COVID-19 in adults with asthma. The study builds on an ongoing study and will be conducted with individuals who have agreed to be recruited for future studies and facilitate recruitment. Furthermore, participants will be drawn from a wide geographic area in the US which increases broad representation of participants. Moreover, we will uniquely gather real time environmental exposure data and indicators of asthma control in unregulated indoor residential space without actual in-person contact. Finally, findings from this study have the potential to impact recommendations for indoor use of disinfectants/cleaners for those with asthma and will guide further research.

References

1. Center for Disease Control and Prevention. Asthma. FastStats web site. <https://www.cdc.gov/nchs/faststats/asthma.htm>. Published 2018. Accessed Date.
2. Center for Disease Control and Prevention. AsthmaStats. https://www.cdc.gov/asthma/asthma_stats/default.htm. Published 2020. Accessed Date.
5. Center for Disease Control and Prevention. Coronavirus (COVID-19). <https://www.cdc.gov/coronavirus/2019-nCoV/index.html>. Published 2020. Accessed Date.

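### Study day (1–14) is neither a named Aim 3 covariate nor a named Aim 1 compliance breakdown, so drift over the two weeks could confound the time-varying associations and a pooled rate could mask fatigue

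*Combined protocol and SAP*

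**What the plan says.** **Aim 3 (Data Analysis).** The model structure is given as "Data collected using the EMA approach are multilevel with time windows (level 1) nested with individuals (level 2"), with no level for day or week. On adjustment the plan says "We will control for level 1 variables (time of day, day of week"), and adds level 2 variables, these being baseline symptoms, demographics and psychosocial measures. Study day is not in the list. The exposures are of three kinds: baseline self-report, weekly counts of VOC and PM2.5 exceedances, and average VOC and PM2.5 levels within time windows.

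**Aim 1 (Data Analysis).** Measures 1a–1c cover response to prompts, spirometer use and modification of the environment. The only breakdown over time is "Compliance as described in 1a-1c by 4-hr each period". The periods are defined at the start of Data Analysis: "Each day of observation will be divided into four 4-hour periods between 6 a.m. and 10 p.m". Differences in use and acceptance are also to be examined by participant characteristics. No table or trend by study day or week is named.

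**Duration and size.** After the run-in, staff "launch the 14-day data collection period" (Procedures, step 3). Under Sample, "Fifty individuals meeting these criteria will be randomly selected and invited to participate in this study". No power calculation is given.

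**The concern.** Day of week is a repeating factor and study day is a running one. A plan that adjusts for the first may look as if it has dealt with calendar time when it has not.

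The protocol gives reasons to expect that calendar time might matter. Participants can see VOC and PM2.5 on the monitor, are alerted when either leaves the optimal range, and are asked 30 minutes later what they did about it (Procedures, steps 5 and 6). Exposure could therefore fall as the fortnight goes on. The outcomes are repeated self-report and self-administered spirometry, which could shift with practice or tiredness. If exposure and outcome both move with study day, a model without study day can attribute the common movement to the exposure.

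The weekly exceedance count is particularly exposed. If it is entered as a weekly value it takes two values per person, so its within-person contrast is simply week 1 against week 2.

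For Aim 1, the course of compliance over the fortnight is one of the things a feasibility study can tell the designers of the powered study. A rate pooled over days does not show it.

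**Working it through.** The plan states no figure on this point, so there is nothing to reproduce. Three checks follow.

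**1. Does day of week absorb study day?**

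The variance of days 1 to 14 is (14² − 1)/12 = 195/12 = 16.25. If everyone starts on the same weekday, removing weekday means leaves each day 3.5 below or above its weekday mean (days 1 and 8 average 4.5, and so on), so the residual variance is 3.5² = 12.25. The share left is 12.25/16.25 = 75.4%. With start days spread at random over 50 people it is about 99.6%, and with balanced start days 100%. Day of week therefore removes at most about a quarter of a linear trend, and probably almost none.

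**2. What could the omission do to Aim 3?**

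From the documents: 50 people, 14 days and 4 periods a day, giving 50 × 14 × 4 = 2,800 person-periods.

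Assumed: 60% of periods observed, all 50 contributing, a true effect of zero, a continuous outcome, linear drift common to all participants, a two-sided 5% test, and drift sizes in within-person SD units.

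Let dx and dy be the total drifts in exposure and outcome from day 1 to day 14. The slopes are dx/13 and dy/13 per day. With 16.25/13² = 0.0962 and start days spread over the week,

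bias = dx·dy·0.0962 / (1 + dx²·0.0962).

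For dx = dy = 1 this is 0.0962/1.0962 = 0.088 SD of outcome per SD of exposure. For dx = dy = 0.5 it is 0.0240/1.0240 = 0.023. If either drift is zero, the bias is zero.

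A simulation (300 runs per row, person-centred linear model with time of day and day of week) gave:

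| Drift, exposure / outcome (SD) | Bias without study day | False positives without | Bias with study day | False positives with |
|---|---|---|---|---|
| 0 / 0 | −0.001 | 5.7% | −0.001 | 5.3% |
| 0 / 0.5 | −0.001 | 6.3% | −0.001 | 7.3% |
| 0.5 / 0 | −0.002 | 4.7% | −0.003 | 4.7% |
| 0.25 / 0.25 | 0.006 | 4.0% | −0.001 | 5.7% |
| 0.5 / 0.5 | 0.021 | 13.3% | −0.002 | 6.0% |
| 1.0 / 0.5 | 0.044 | 47.0% | −0.001 | 5.3% |
| 1.0 / 1.0 | 0.088 | 95.7% | −0.001 | 3.7% |

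The standard error of a 5% rate from 300 runs is √(0.05 × 0.95/300) = 1.3 percentage points, so the rates between about 4% and 7% are compatible with the nominal level.

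The rows describe a window-level exposure and a continuous outcome such as FEV1% predicted. The logistic models and the weekly counts were not simulated.

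**3. What could a pooled compliance rate conceal?**

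For a straight-line change over 14 days, the overall rate is the mean of the first and last values. The week means lie three daily steps in from the ends.

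| Course | Overall | Week 1 | Week 2 |
|---|---|---|---|
| Flat 70% | 70% | 70% | 70% |
| 80% to 60% (step 20/13 = 1.54) | 70% | 75.4% | 64.6% |
| 90% to 50% (step 40/13 = 3.08) | 70% | 80.8% | 59.2% |

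A table by four clock periods cannot tell these apart if the decline is similar at all times of day. The courses are illustrations, not predictions.

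**The case against.** The other side has several sound points.

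- **Drift is not shown.** A reader might infer that Aim 3 is confounded. The documents do not support that: they report no 14-day trend in exposure, symptoms or spirometry. Alerts and a follow-up survey show that short-term responses are expected, which is not the same as a progressive change. Both sides must drift, and at 0.25 SD each there is no visible inflation. This stands, and makes the point conditional.
- **Not every exposure is affected.** Baseline self-reported exposure is fixed within a person and cannot share a within-person trend. This stands.
- **There are partial safeguards.** The 3-day run-in and in-app spirometry coaching should reduce early practice effects. Staff contact participants after a 24-hour data gap and check in at about day 7. The plan also covers duration of monitor use and daily VOC and PM2.5 averages. These help, but none adjusts Aim 3 for study day or reports response rates by day.
- **Fatigue is not hidden for good.** A reader might infer that a decline in compliance could not be detected. The data are time-stamped, so it would be unreported rather than unrecoverable.
- **The compliance wording has another reading.** The 4-hour breakdown most naturally means four clock periods. It could mean all 4 × 14 = 56 periods per participant, which would show fatigue. The text should say which.
- **The advisory board did not leave an open objection.** The Chicago Asthma Consortium paragraph lists "the 14-day data collection length" among the feedback topics and says that suggestions were incorporated. It records no unresolved worry about duration.
- **Aim 3 is exploratory.** This lowers the stakes of a false positive, but the results are still meant as preliminary data for a powered study.

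**Conclusion.** Both omissions are real: no study-day term in the Aim 3 covariates, and no compliance breakdown by study day or week in Aim 1. Day of week does not fill the gap.

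The consequence for Aim 3 is a possible bias, confined to the window averages and weekly exceedance counts. It is nil if only one side drifts, negligible at joint drifts of 0.25 SD, and material from roughly 0.5 SD upward. Those thresholds rest on the assumed linear drifts, 60% of periods observed and a continuous outcome; the documents supply none of these.

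The Aim 1 half is the stronger one, because feasibility is the study's main purpose and the gap there needs no assumption about bias. As most naturally read, the planned tables would not distinguish steady from falling compliance.

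The change is worth making because it costs almost nothing, not because the present analysis has been shown to be wrong.

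**What to change.** - **Aim 3:** add study day (linear, or week 1 versus week 2) to the level-1 covariates in the models with time-varying exposures. Models whose only exposure is baseline self-report do not need it for this purpose. A common linear term removes only the average trend, not trends that differ between people, and the plan should say so. With a week term in the model, the within-person information in a weekly exceedance count comes only from differences between people in how their counts changed.
- **Aim 1:** tabulate measures 1a–1c by study day as well as by 4-hour period, and state whether the 4-hour breakdown means four clock periods or all 56 periods.

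The cost is one covariate and one table from time stamps already collected, with no added burden on participants.

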1. *Adult Asthma History* includes 5 items adapted from the Behavioral Risk Factor Surveillance System Survey.⁷⁴ Four items address participants' recent contact with healthcare professionals for asthma since COVID-19. The final item addresses changes in routine work/activities due to asthma since COVID-19.
2. *Asthma Control Test (ACT)*. The ACT includes 5 items addressing: asthma symptoms, use of rescue medications, and effect of asthma on daily functioning. Responses are summed for total ACT score.^{75,76}
3. *Airborne Exposures*. The 7 items from the PROMISSM Pool V1.0 Dyspnea Airborne Exposure address airborne allergens, pollutants, smoke, pets, and use of pesticides using Yes:No response options.⁷⁷
4. *Adult Asthma Adherence Questionnaire*,TM includes 5 items on following their prescribed asthma medication plan and barriers to following that plan.⁷⁸
5. *Health and Demographics* includes items such as self-rated physical health, comorbidities, height/weight, age, education, ZIP code, smoking status, and COVID-19 prevention practices, and COVID-19 exposure/infection status.
6. *Home Environmental Exposure* data will be gathered including home type, # of occupants, vacuum with HEPA filter, cleaning practices, cleaning products, air filter, heating, ventilation, smoke exposures, hand washing practices, pests, hobbies, odors, indoor plants, printers, flooring, and stove type.^{79,80}

We will also measure the following psychometrically valid measures as potential confounders:

7. *Emotional Distress-Anxiety and Depression PROMIS Short Forms 4a* assess anxiety and depression levels within the last 7 days (4 items). Higher scores indicate higher severity of anxiety or depression.^{81,82}
8. *Emotional Support*, PROMIS_SF_V2 Short Form 4A measures perceived feelings of support, being cared for and valued (4 items).⁸³ Higher score indicating a higher perceived emotional support.
9. *Perceived stress scale* includes 4 items measuring the degree to which situations in one's life are appraised as stressful.⁸⁴⁻⁸⁶ Higher scores indicate an increased level of perceived stress.

EMA survey items (See Appendix).

- *Asthma symptoms* (trouble breathing, wheezing, coughing, other symptoms [Yes:No]) assessed each time participants are asked to complete an EMA survey.
- *Random EMA surveys (twice/day)* assess use of disinfectants/cleaners in last 2 hours (Yes:No) if Yes, the type, brand, and asthma symptoms are queried.

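### Medication adherence is measured at baseline but left out of the Aim 3 level-2 covariates, so between-person exposure estimates may carry residual confounding by adherence

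*Combined protocol and SAP*

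**What the plan says.** Baseline Measures, item 4, is an adherence questionnaire that "includes 5 items on following their prescribed asthma medication plan and barriers to following that plan". Items 7 to 9 (anxiety and depression, emotional support, perceived stress) then follow under their own lead-in: "We will also measure the following psychometrically valid measures as potential confounders". Adherence stands before that line and is not given the label.

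Data Analysis, Aim 3, gives the adjustment set in one sentence. At the window level: "We will control for level 1 variables (time of day, day of week". At the person level: "level 2 variables (baseline asthma symptoms, demographic characteristics, and psychosocial characteristics". Neither adherence nor medication is named. No other stated analysis names the adherence score. The nearest is Aim 1, which compares use and acceptance across an open-ended list of participant characteristics.

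The same section lists three exposures:

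- (1) "Baseline self-reported use and frequency of disinfectant/cleaner use", together with baseline PM2.5 exposures
- (2) "Number of times VOC and PM_{2.5} levels exceed the threshold for the optimal readings per week"
- (3) "Average scores of VOC and PM_{2.5} levels in the time windows considered in the analysis"

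The outcomes are any asthma symptoms, inhaler use and FEV1% predicted.

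**The concern.** All three outcomes can plausibly depend on whether a participant takes prescribed asthma medication, and the study does not standardise treatment. Under Procedures, step 5, participants with symptoms follow their own action plan or provider's instructions.

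Exposure (1) has one value per person. Exposure (2) has at most two, because data collection lasts 14 days. Exposure (3) varies within a person, but no person-mean centring is stated, so its coefficient mixes within-person and between-person information. A random intercept does not remove confounding from between-person contrasts. Only the named level-2 covariates can do that.

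If adherence is associated with exposure given those covariates, some of its effect on the outcomes will be read as an exposure association. The Specific Aims intend the findings as preliminary data for a later powered study, and the Summary says they could affect recommendations on indoor use of cleaning products. A person-level association that partly reflects medication-taking would be a weaker basis for either.

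**Working it through.** The plan states no power, alpha, effect size or sample-size calculation, so there is no figure to reproduce. The check has two parts.

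**1. Baseline measures against the Aim 3 covariates.** The psychosocial group in the model matches items 7 to 9, which carry the confounder label. The baseline-symptom term may be the Asthma Control Test (ACT, item 2), though the plan does not say so. Demographics are in item 5. Adherence (item 4) matches none of the three groups on a natural reading, although the groups are not itemised and nothing excludes it expressly.

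**2. Possible size.** Take a linear person-level model with all variables standardised and no true exposure effect.

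From the documents:
- 50 participants (Sample)
- adjustment for baseline symptoms (Aim 3)

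Assumed, because the documents give no values:
- r, adherence-exposure correlation (magnitude): 0 to 0.3
- b, standardised effect of adherence on outcome: 0.3, with 0.5 as a sensitivity value
- c, adherence-baseline symptom correlation: 0 to 0.5
- exposure related to baseline symptoms only through adherence
- about 8 level-2 covariate degrees of freedom
- two-sided 5% test

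The bias in the exposure slope is b times the coefficient of adherence on exposure given symptoms:

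bias = b × r(1 − c²) / (1 − r²c²)

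SE ≈ 1/√(50 − 1 − 1 − 8) = 1/√40 = 0.158

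For r = b = 0.3:
- c = 0.5: 0.3 × 0.3 × 0.75 / (1 − 0.0225) = 0.069, and 0.069/0.158 = 0.44 SE
- c = 0: 0.3 × 0.3 = 0.090, and 0.090/0.158 = 0.57 SE

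Rejection rate = P(Z > 1.96 − bias/SE) + P(Z < −1.96 − bias/SE). In each range below the lower end is c = 0.5 and the upper end c = 0.

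| r | b | bias | bias/SE | rejection at nominal 5% |
|---|---|---|---|---|
| 0 | any | 0 | 0 | 5.0% |
| 0.1 | 0.3 | 0.023–0.030 | 0.14–0.19 | 5.2–5.4% |
| 0.2 | 0.3 | 0.045–0.060 | 0.29–0.38 | 6.0–6.7% |
| 0.3 | 0.3 | 0.069–0.090 | 0.44–0.57 | 7.2–8.8% |
| 0.3 | 0.5 | 0.115–0.150 | 0.73–0.95 | 11–16% |

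At r = b = 0.3, adjusting for a symptom score correlated 0.5 with adherence removes about a quarter of the bias (0.090 to 0.069).

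**Direction.** If careful patients both take medication reliably and limit exposures, exposure would look more harmful than it is. Selection could work the other way. Entry requires an ACT score of 19 or less, and the Preliminary work section reports that more frequent disinfectant use went with scores in that range. Suppose exposure correlates 0.3 with worse control, adherence correlates 0.3 with better control, and the two are unrelated in the population. Conditioning on control then gives them a partial correlation of 0.09/0.91 ≈ 0.10, opposite in sign to the careful-patient pattern. The sign is therefore not known in advance.

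**The case against.** A reader might infer that the Aim 3 exposure estimates are confounded by background treatment. The documents do not support that, for four reasons:

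- Confounding needs adherence to be associated with exposure given the covariates, and no such figure is given. At r = 0 there is no bias.
- Eligibility requires disinfectant or cleaner use at least five times a week. Low users are screened out, which weakens the careful-patient argument for the disinfectant contrast, though not for PM2.5 or smoke.
- Adherence is not background treatment. The baseline measures as described name no controller type, dose or treatment step, so a person fully adherent to minimal therapy scores like one fully adherent to intensive therapy.
- Within-person variation in window-average VOC and PM2.5 cannot be confounded by a fixed baseline score, so not every Aim 3 estimate is exposed.

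Baseline-symptom adjustment may also capture part of the adherence effect, especially if the ACT is used: "The ACT includes 5 items addressing: asthma symptoms, use of rescue medications, and effect of asthma on daily functioning". An ACT score of 19 or less is a range, not a constant. This stands, but the working shows that the capture is only partial.

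Adherence is recorded at the same time as exposure (1) and might itself respond to exposure-related symptoms, in which case adjusting would over-adjust. This is a reason to show both estimates, not to leave the variable unused.

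Finally, Aim 3 is exploratory, in a 50-person feasibility study with no stated alpha. A reader might also infer that an Aim 3 coefficient will be carried directly into the later study. The documents say only that the findings provide preliminary data.

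**Conclusion.** The gap is real but modest. A baseline variable plausibly related to all three outcomes is collected and then named in no analysis, while two of the three exposures are wholly or mainly between-person. Those estimates, and the between-person part of the third, may carry residual confounding by adherence.

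Under assumed associations of 0 to 0.3 with exposure and 0.3 with outcome, after baseline-symptom adjustment, the bias is between none and about 0.6 SE, with a nominal 5% test rejecting about 5 to 9% of the time. It approaches one SE only if the outcome effect is raised to 0.5. These figures rest on assumed inputs and a linear person-level approximation. They show what is possible, not what is expected. What is affected is the interpretation of exploratory estimates, not a confirmatory result.

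**What to change.** In Data Analysis, Aim 3, itemise the level-2 covariates and add the Adult Asthma Adherence Questionnaire score to every model that includes a person-level exposure. That includes the window-average models as long as their coefficient mixes within-person and between-person variation. State how the questionnaire is scored, since it covers both following the plan and barriers to doing so. Report the exposure estimates with and without the adherence term. Adherence should join the psychosocial scales, not displace them: the documents give no basis for ranking it above measures the plan itself designates as confounders.

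The data are already collected. With a single score the cost is one level-2 degree of freedom, an SE factor of √(40/39) ≈ 1.01. Collinearity adds a factor of at most 1/√(1 − 0.3²) ≈ 1.05 over the assumed range. Together that is at most 1.013 × 1.048 ≈ 1.06, before any gain from lower residual variance. The change adjusts for adherence only, as far as the questionnaire measures it. Controller type and intensity stay unadjusted, and the estimates stay exploratory.
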